The study team members and operation theatre staff will conceal the group assignment from the subjects, the medical and paramedical staff outside the operation theatre and surgeons prior to operation. The operation theatre attendants will be specially trained to create noises during the operation of both groups so that the subject in theatre or relatives outside the theatre cannot predict the group. The medical officer of the study team carrying out follow up of the subject postoperatively and after discharge will also be kept unaware of the group allocation.

At the end of study, the Principal surgeon will send the random number list, to the statistician of the study replacing the groups with any two alphabets (to blind the study for the statistician).

An independent statistician from another institution will perform the primary analysis of our randomized controlled trial. The subjects of the study will be completely blinded to the intervention and they will never be given any information about their study group, neither before nor after the operation.

Interventions

All the volunteers will receive standard preoperative care i.e. antibiotic cover with injection ceftriaxone 1gram IV stat and C-section under spinal anaesthesia. All the women will be catheterized before the operation.

Catheterization:

The women will be catheterized under spinal anaesthesia. We will train theatre staff nurses to perform catheterization for cysto-inflation. The staff nurse will perform catheterization after scrubbing and wearing sterilized gloves. First of all, one of the primary surgeons will clean the abdomen, legs and perineum for C-section with Povidone-iodine. Then the subject will be put in supine position (with legs spread and feet together) for catheterization. The staff nurse will clean urethral meatus and labia with three small gauzes soaked in a bowl of sterile water. She will separate the labia with left hand and clean the urethral meatus from front backwards with the wet gauze piece held with sterilized sponge holder. After cleaning one-time, she will waste that gauze and clean the labia in the same way with the two other sterilized gauze pieces. After this, one of the primary surgeons will hold the ports and tubing of the catheter high above the perineum while the staff nurse will hold the tip of the catheter and insert the catheter into urethra well beyond the Foleys bulb without touching it elsewhere and hold it

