there while the surgeon holding the tubing will inflate the balloon of the urinary catheter with 10cc distilled water. The theatre attendants will then correct the position of the patient again to straight leg position. The urinary catheter will be kept elevated as long as the patient will be draped with sterilized sheets for operation by the other surgeon. Then, the catheter end near the urinary port will be fixed to the patient sheet in front of the thigh to carry out cystinflation conveniently and attached to the urine bag for drainage.

Adhesiolysis

If adhesions will be encountered during opening the peritoneal cavity or before the separation of bladder flap, the primary surgeons will hold the operation and call the principal surgeon to carry out adhesiolysis and complete the operation. The Principal surgeon will grade the adhesions according to Tulandi's classification and if the woman will fulfil perioperative criteria for adhesions, the Principal surgeon will enrol her in the study as subject and perform randomization into cystoinflation and control groups according to her random number envelope. Adhesiolysis will be performed with the inflated bladder in cystoinflation group, and with the empty bladder in the control group.

Cystoinflation group: The adhesiolysis in cystoinflation group will be performed by bladder retro-fill. Cystoinflation (bladder retrofill) will require normal saline drip and a 60cc bladder wash syringe and an artery clip. In cystoinflation group, the bladder will be retro-filled with 300cc saline by the assigned house officer under strict aseptic measures at the rate of 60cc in one minute. Meanwhile, the principal surgeon will identify the margins of the bladder among adhesions. The catheter will be clamped with an artery clip after filling the bladder with 5 fillings of the syringe. The surgeon will stretch the adhesions by upward traction on the surface of the uterus with a sponge and counter-traction on adhesion with elices forceps or sponge and perform adhesiolysis by sharp dissection with a fine dissecting scissor. The adhesiolysis will be performed until the bladder surface can easily be pushed down. Thereafter, the house officer will attach the urine drainage port of the catheter with the tubing of the urine bag and remove the artery clip to empty the bladder. The surgeon will then push the bladder downward with Doyen's retractor to improve visualization in the surgical field and complete the C-section.

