 - i. The size of the injury will be measured in centimetres with a sterilized scale.
 - ii. The site of injury can either be the dome of the bladder, the posterior bladder wall, the trigone or one or both ureters.
 - iii. Depth of injury will be taken as layers involved i.e. either involving muscular layer partly or completely with intact mucosa or full depth injury (perforation).
 - iv.

Operative Time: The staff nurse will record the duration of surgery as time in minutes from incision to closure of the skin.

Blood Loss: The estimated blood loss will be determined by the increase in weight of sponges used during the operation, taking 1 gram equal to 1cc of blood and the number of subjects who received blood transfusion during operation.

Secondary Outcomes

Postoperatively, subjects will be assessed for urinary tract infection (UTI), micturition problems, and fistula formation during the hospital stay and for the next three months. Duration of catheterization and hospital stay will also be recorded. The outcome of each subject will be noted on a Performa by assigned medical officers during the hospital stay and the follow-up period and entered in SPSS20 datasheet.

1-Urinary tract infection (UTI) markers will be more than 10pus cells/hpf in urine or urine showing infectious organisms on culture on the third postoperative day.

- A. **Dysuria** will be expressed by the subject as painful micturition using an 11point Numeric Rating Scale ICCs (.673-.825), $r=.7-.99$. (0 No Pain, 1-3 Mild Pain, 4-6 Moderate Pain, 7-10 Severe Pain).
- B. **Other micturition problems** (feeling of incomplete evacuation, frequency, urgency, urethral and extra-urethral incontinence) will be measured subjectively on Likert scale questionnaire (0-never, 1-rarely, 2-sometimes, and 3-often) and analyzed as a composite variable in spss. Urinary retention will be diagnosed if post-micturition bladder volume is >50cc on ultrasonography on the day of discharge from the hospital.

- I. **Feeling of incomplete evacuation:** It is the feeling created by incomplete emptying of the bladder. The subject will be inquired about the feeling of full bladder accompanying it.
- II. **Urgency** will be diagnosed as a sudden urge to urinate.
- III. **Frequency** Needing to pass urine more than seven times in 24hours.

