- IV. **Vesicovaginal or uretro-vaginal Fistula:** In subjects with the complaint of urinary incontinence, the fistula formation i.e. abnormal communication of urinary bladder or ureter with vagina will be ruled out by three swab test and retrograde cystography. The follow up of fistula cases is outside the scope of this study so it will not be included in description or analysis.

C. **Duration of Foleys catheter and hospital stay:** The Foley's catheter will be removed after 24 hours in distension arms of both groups and subjects stay in the hospital for four days. In the bladder injury arms, the catheter will be kept in situ for 7days to give rest to the bladder for the healing of repair of muscularis disruptions, for 10 days in case of repair of perforations smaller than 1cm, and for 14 days for repair of perforations greater than 1cm. After removal of the catheter, the subjects will be kept in the hospital for twelve hours and then discharged if there will have no subjective urinary complaint.

The finding of subjects will be noted on output form by assigned trainees. The participant's first entry on follow up form will be completed on the third postoperative day; second entry will be at the time of discharge from the hospital and last entry at the end of three months postoperative period. In between, they will be advised to visit our team whenever a problem emerges during the postoperative period and their findings will be recorded on the output form. In subjects complaining of urinary incontinence, the fistula formation will be ruled out first by three swab test and then by retrograde cystography. The postoperative visit at the end of 3months will be mandatory. During this visit, all the subjects will be analyzed for postoperative micturition problems and their retrograde cystography will be performed to rule out fistula formation. The subjects with fistula will be referred to the urologist for further management. The last entry at the end of three months will also be mandatory for the inclusion of participant outcome after discharge in results. The participants will be advised to visit the researcher team at the end of 3months period. They will be reminded for their visit on phone call after week if they do not come for follow-up (See [Outcome](#)).

Statistical analysis

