We will perform Statistical analysis by using IBM spss statistics 20 (SPSS Inc, Chicago, IL, USA). The characteristics of the subjects will be analyzed as continuous data or ordinal data. Normality of continuous data will be analyzed by the Shapiro Wilk test. The normal baseline data will be compared by T-test, non-normal data by Mann Whitney U test and ordinal data with the chi-square test. The outcome of both groups will be calculated as numbers (percentages) by descriptive statistics. The effect of cysto-inflation on outcome data will be analyzed using regression analysis. The same problem experienced by the same subject will be recorded only once on the spss datasheet. There will be no second entry if the subject presents with the same problem again. The data for any subject who do not come for follow up after discharge will be used and analyzed in study characteristics but will be excluded from the analysis of results. The power of the study for bladder injury will be calculated with statistical software G'Power version 3.1.

Adverse events

The study team will be responsible to record all adverse events and serious adverse events to the subjects of the study, related to or not related to the intervention. The team members will ask open probing questions to enhance the quality of the collected data. An adverse event is

defined as any undesirable experience during follow-up leading to contact with the healthcare system (general practitioner or hospital). If adverse event results in hospitalisation, prolonged inpatient hospital care, result in re-surgery, or if an adverse event is life-threatening, result in death, permanent disability or damage, they will be categorised as serious adverse events. Adverse Events will be recorded in the adverse events reporting register. The study team will report all expected and unexpected adverse events in the study population to the principal investigator in monthly meetings to assess their potential consequences.

Data Management Plan

Documents safety

All the documents, together with the numbered envelopes and the completed forms will be stored in folders that will be kept in the locked research office of the principal investigator with access limited to authorised persons. The study team will ensure that all variables from the completed forms are continuously entered into SPSS 20 datasheet.

Data monitoring

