The study will not have a formal data monitoring committee as no serious adverse events are related to or have been observed previously by implication of this intervention in the hospital. Any unexpected serious adverse events or outcomes will be discussed by the trial management committee (study team). Furthermore, the trial management committee will monitor recruitment, intervention and follow up rates and any concerns related to the study.

Data safety

Once the trial is completed, all material belonging to the study will be stored in the research office. Collected data will be retained in the custody of the principal investigator till compilation of results by statistician so that any missing piece of information can be acquired from the data file.

Data Destruction Plan: To minimize the risk of breach of confidentiality, we will not use the subject's name or hospital number to identify them on any study records. Instead, a study number will be assigned to each subject according to the random number envelope. This number will be used to study documents that relate to the subject and to enter data in spss. We will keep the list of random number groups in a secure, locked location. At the end of the project, this list will be destroyed. All personal data will also be destroyed at the end of the trial to protect confidentiality before, during and after the trial.

Quality assurance: The study team will arrange a monthly quality assurance meeting with the principal investigator. All the problems faced during the consent, theatre management and conducting the postoperative surveys of the patient will be discussed. The solutions should be sought for each problem and refinements will be implemented if needed. The data collection and management procedures of the study have been approved by the king Edward medical university, Pakistan.

Ethics, dissemination and perspectives of the study

Ethics

The study is a part of the project "Cysto-inflation Versus deflation to prevent bladder injury in OBG (obstetrics and gynaecology) surgery" approved by the ethical committee of King Edward Medical University, Pakistan with ERB#216/RC/KEMU on 27 March 2017 and will be conducted in accordance to the Helsinki declaration. Personal information about patients will be kept separate from the main dataset and will not be shared.

Dissemination

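### The adverse event definition leaves out events during surgery, when the bladder is filled, and does not settle whether the index hospital stay counts

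*Combined protocol and SAP*

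**What the plan says.** The Adverse events section opens with a broad duty: the team is to "record all adverse events and serious adverse events to the subjects of the study, related to or not related to the intervention". It then gives the plan's only definition of an adverse event, "any undesirable experience during follow-up leading to contact with the healthcare system (general practitioner or hospital". Serious events are drawn from within that set: "If adverse event results in hospitalisation, prolonged inpatient hospital care, result in re-surgery", followed by life-threatening events, death and lasting disability or damage. Events go into an adverse event register and are reported to the principal investigator at monthly meetings.

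The Data monitoring section states: "The study will not have a formal data monitoring committee as no serious adverse events are related to or have been observed previously". Unexpected serious events or outcomes are to be discussed by the study team acting as management committee.

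The intervention is described in the Adhesiolysis section. In the cystoinflation group "the bladder will be retro-filled with 300cc saline by the assigned house officer under strict aseptic measures", adhesiolysis is done with the bladder full, and the bladder is emptied before the caesarean is completed.

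**The concern.** The definition has a time window and a trigger, and neither suits an intervention that starts and ends on the operating table in women who are already admitted. If staff apply the wording as it stands, an event in the period when bladder filling could cause harm need not be classed as adverse. It then cannot be classed as serious either.

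The register and the monthly reports are at stake. With no formal monitoring committee, they are the main safety review, and they depend on what is classified as an adverse event. A low or zero count of serious events at the end of the trial would be hard to interpret if the definition did not reach the operation.

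**Working it through.** The plan states no figure on this point, so the check sets the definition against the rest of the text.

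**1. The conditions.** An adverse event needs both (a) occurrence during follow-up and (b) a resulting contact with a general practitioner or hospital. A serious event needs (a), (b) and a seriousness criterion.

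**2. The operation.** The fill is five syringes of 60cc at 60cc a minute: 5 × 60 = 300cc, about five minutes, followed by adhesiolysis and emptying. Women are randomised during the operation, just before this. The Data collection procedure section names surgery as a time point of its own, and no section or form heading calls it follow-up. An intraoperative event fails (a). It also does not fit (b), since the woman is already in hospital.

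**3. The index hospital stay.** The plan's uses of follow-up do not agree:

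| Place | Wording | Is the stay follow-up? |
|---|---|---|
| Secondary Outcomes | "noted on a Performa by assigned medical officers during the hospital stay and the follow-up period" | No, named separately |
| Blinding | "carrying out follow up of the subject postoperatively and after discharge" | Yes |
| Follow-up schedule, after the paragraph on catheter duration and hospital stay | "first entry on follow up form will be completed on the third postoperative day" | Yes; the planned stay without injury is four days |
| Outcome Form | The day-3 and discharge-day sections are both headed as postoperative follow-up | Yes |

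Condition (a) is therefore ambiguous for the stay. Condition (b) fits badly on either reading, because an event on the ward does not bring an inpatient into contact with a hospital.

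**4. After discharge.** Condition (a) is met. Condition (b) still removes any event for which the woman sought no care.

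**5. Internal consistency.** The opening duty covers all events, related or not, and sets no time limit. The seriousness criteria include prolonged inpatient care and re-surgery. Both can arise in the index admission, so the criteria suggest that inpatient events were meant to count. The definition does not deliver this.

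**6. What is collected by another route.** Bladder injury with its size, site and depth, operative time, blood loss and transfusion are primary outcomes. Urinary infection, retention, micturition problems and fistula are assessed as secondary outcomes. Fever has its own line on the Outcome Form. The form as shown has no line for bowel injury, anaesthetic events, return to theatre or a problem with the retro-fill, and no free-text adverse event line. The Statistical analysis section does not mention tabulating adverse events by arm.

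**7. Extent.** 2 × 107 = 214 planned operations fall in the uncovered window. The documents give no rates for the events in step 6 that lack a form line, so the number that might be missed cannot be calculated.

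**The case against.** The strongest reply is that the plan shows a clear intention to capture everything. It has a duty to record all events, a separate register, probing questions to participants, monthly reporting of expected and unexpected events, referral of unexpected serious events or outcomes to the management committee, and a provision under anticipated problems for stopping the study after an unexpected outcome. The harms most likely to follow from filling a bladder among dense adhesions are already outcomes. On this view the definition is loosely worded and a sensible team would record a bowel injury anyway.

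Much of that stands. The main expected harms are not lost, and a missing line on the Outcome Form does not show that an event would go unrecorded in the register. But the register holds adverse events, and the only rule for what counts as one excludes the operation as written. The broad duty does not cure this, because it uses the same defined term.

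A reader might go further in three ways that the documents do not support.

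- **That the whole hospital stay is excluded.** The Blinding section, the follow-up schedule and the form headings treat inpatient assessments as follow-up, and the seriousness criteria point the same way. The stay is unclear, not excluded.
- **That repaired bladder injuries with a longer stay would vanish from the safety record.** Bladder injury is the first-listed primary outcome and is reported by group. The Secondary Outcomes section also says that catheter duration and hospital stay will be recorded, although the form as shown has no line for either. These women should not be counted as missed harms.
- **That the decision to have no monitoring committee rests on this definition.** The Data monitoring section bases that decision on earlier use of the technique in the hospital, which this trial's definition could not have shaped.

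**Conclusion.** The point holds in a limited form. Events during surgery do not meet the adverse event definition and so cannot be serious adverse events. Coverage of the index admission is unresolved because follow-up is used in two senses and the contact condition does not suit inpatients. Both conflict with the section's own duty to record all events and with its criteria of prolonged inpatient care and re-surgery.

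The consequence is confined to events that are not already outcomes or Outcome Form items, and to what reaches the register and monthly reports. The primary analysis is unaffected. The window concerns all 214 planned operations, with no defensible count of missed events.

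This conclusion assumes that the definition is applied as worded; staff who followed the evident intention would miss less. It matters more than a wording slip usually would because the excluded period is when the intervention acts and there is no formal committee looking at other data.

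**What to change.** - Define an adverse event as any undesirable event from randomisation to the three-month visit, whether or not it leads to new healthcare contact.
- State that the operation from randomisation onward and the index admission are included, and that the seriousness criteria apply in both.
- Add a free-text adverse event line to the operative, day-3 and discharge sections of the Outcome Form.
- Tabulate adverse and serious adverse events by arm, and say so in the Statistical analysis section.

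The cost is a change of definition wording, three form lines, a table and slightly more recording. One precaution follows from the Blinding section. An operative entry about the retro-fill would reveal the group, so the operative section should be kept apart from the sheets used by the follow-up medical officer. The change does not touch treatment, sample size or the analysis of the outcomes.

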Control group: The subjects assigned to the control group will undergo no intervention. The Principal surgeon will perform adhesiolysis by the same traction counter-traction method with urinary catheter put on free drainage throughout the C-section.

If there will be a suspicion of bladder injury in either group, it will be confirmed by performing the retrograde dye test with methylene blue and injury will be repaired by the Principal surgeon.

Crossover

There is no possibility of crossover in this study as subjects will be selected during operation and the women who refuse to be included in either group preoperatively will be excluded from the study before group assignment.

Data collection procedure

Data will be collected at the time of admission (baseline), during surgery, on the 3rd postoperative day, at the time of discharge from the hospital and the end of three month follow-up period (for those enrolled in the study). The subjects will be advised to report for any postoperative fever or micturition problem during follow-up. Their visits will be recorded on follow up form by the study team medical officers specifically trained in correctly interpreting the problems of the subjects and filling the outcome form (See [Outcome](#) Form).

Baseline Data

The entry form will include baseline data consisting of demographic features and characteristics of the subjects recruited in the study. The demographic features will include age, gestational age, parity, socioeconomic status, and the number of previous C-sections. The other characteristics will be the score of adhesions and preoperative postmicturition bladder volume. The allotted random number will be entered in entry form of the subject and will be signed and kept in a locked place by study team manager in the theatre. (See [ENTRY FORM](#))

Outcome

Primary outcomes will be the bladder injury rate, the extent of the injury, operative time, blood loss and proportion of subjects receiving blood transfusion.

The bladder injury: The bladder injury will be detected by direct observation during surgery. The suspected bladder injury will be confirmed with the dye test and will be reported as the bladder injury rate and extent of injury.

- A. Bladder injury rate will be recorded as the percentage of subjects with bladder injury in each group.
- B. The extent of the injury will be analyzed by the size, site and depth of injury.

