[name] is the Corresponding Author and chief investigator. She has conceived the project and she will write and review the manuscript and will create Figures and tables. She will hold a monthly meeting of the research team to evaluate any difficulties encountered with study design and to find a solution to the problems.

[name] will counsel the subjects, participate in preparing random numbers file, conduct surveys to collect preoperative and postoperative data in wards, participate in Manuscript writing and review the manuscript.

[name] will counsel the subjects, participate in preparing random numbers file, manage cysto-inflation in theatre, perform follow up of the subjects and conduct the survey in the hospital to collect data after discharge, and will review the manuscript.

[name] will collect all preoperative and postoperative data, enter it into SPSS data sheet and hand it over to statistician and review the manuscript.

[name] will perform statistical calculations and will review the manuscript.

Collaboration with other scientists: To avoid Bias, the research team will shift data in spss datasheet to [name] for the compilation of results on an individual level.

A randomized controlled trial of CystoInflation to prevent bladder injury in the adhesive disease of multiple caesarean sections

ENTRY FORM OF CYSTOINFLATION STUDY

Country	Pakistan
Hospital	Lady Willingdon Hospital
Unit	1

Patient Profile

Patient name	
Age	
Gestational age	
Parity	
Socioeconomic status	
BMI	

Examination

Pulse	
BP	
Temperature	
Pallor	
Chest	
CVS	
P/A	

Investigations

Blood Group	
C/E blood	
C/E Urine	
BSL(F)	
Obstetric USG	

Randomization

Date of operation	
Time of operation	
Grade of adhesions	
Eligible	
Consent for study	
Random number	
Signature of the Principal	

surgeon	
---------	--

- Store the original completed form in the Principal investigator study file.

A randomized controlled trial of Cysto-inflation to prevent bladder injury in the adhesive disease of multiple caesarean sections

OUTCOME FORM

Operative Findings

Bladder injury	No	Yes
Size		
Site		
Depth		
Operative time		
Blood loss		
blood transfusion		
Operative time		
Blood loss		
blood transfusion		

Postoperative Follow up on 3rd postoperative day

Follow up	No	Yes
WBC count		
Urine culture	_ive	+ive

fever	No					Yes					
Dysuria	0	1	2	3	4	5	6	7	8	9	10
Frequency of micturition	0				1			2			3
Urgency of micturition	0				1			2			3

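### The duty list gives follow-up to the team member who manages cystoinflation in theatre, which conflicts with the promise of an assessor who does not know the group

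*Combined protocol and SAP*

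**What the plan says.** All references are to the combined protocol and SAP.

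- **Blinding.** The study medical officer "carrying out follow up of the subject postoperatively and after discharge will also be kept unaware of the group allocation".
- **Project Management.** One member counsels women, takes part in preparing the random numbers file, and is also to "manage cysto-inflation in theatre, perform follow up of the subjects and conduct the survey in the hospital to collect data after discharge". A second member counsels, shares the preparation of that file and surveys women on the wards before and after operation. A third "will collect all preoperative and postoperative data, enter it into SPSS data sheet and hand it over to statistician".
- **Interventions.** In the cystoinflation group "the bladder will be retro-filled with 300cc saline by the assigned house officer under strict aseptic measures". For controls: "The subjects assigned to the control group will undergo no intervention"; adhesiolysis is done "with urinary catheter put on free drainage throughout the C-section".
- **Data collection procedure.** Follow-up visits are recorded "by the study team medical officers specifically trained in correctly interpreting the problems of the subjects". Secondary Outcomes names assigned medical officers in one place and assigned trainees in another.
- **Randomisation procedure.** Study team medical officers in theatre write each woman's random number on her documents, including the Outcome Form.

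**The concern.** The trial has no sham, so blinded follow-up depends on keeping the people who question the women apart from the people who see the operation or handle the allocation. The Blinding section promises this separation, but the duty list does not provide it.

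The outcomes at stake matter to the trial's own argument. The Background says that over-distending the bladder carries a risk of micturition problems afterwards, and the follow-up symptoms are how the trial would show whether retrofill causes them. An interviewer who knows which women had retrofill may probe harder, or record borderline complaints differently, in one arm. The direction cannot be predicted: it could inflate complaints after retrofill or play them down. If nothing changes, the report would describe follow-up as blinded when the trial's own assignment of duties says otherwise.

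**Working it through.** No plan figure needs reproducing. The check sets the sections side by side.

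1. **Same person, both roles?** Yes. The duties stand in one sentence about one member: "participate in preparing random numbers file, manage cysto-inflation in theatre, perform follow up of the subjects".
2. **Does the theatre role reveal the arm?** Yes. The 300 cc retrofill happens in one group only. Controls have no filling and no imitation of it. A house officer does the filling, but whoever manages the procedure in theatre still learns which women had it.
3. **Does any masking cover this person?** No. The noises made in theatre are meant to mislead the woman and her relatives. The concealment duty protects staff outside theatre and, before the operation, the surgeons.
4. **Does another passage move the follow-up elsewhere?** No. Medical officers, trainees and the member who collects all data are also named. These assignments overlap with the theatre member's follow-up and survey and do not cancel them. Study team medical officers appear both in theatre and as recorders of visits, with no stated mechanism to keep the two sets apart.
5. **Is ward follow-up safer?** Not securely. The ward surveyor helps prepare the file that pairs numbers with groups, and the random number is on the Outcome Form. Someone who helped make the file could link the two.
6. **Which data depend on the interviewer?**
   - Dysuria (0-10) and the Likert micturition items (0-3), which are analysed as a composite.
   - Adverse events, which the team elicits with open, probing questions (Adverse events).
   - Fever, which is on every follow-up page of the Outcome Form.
   - Steps triggered by a complaint: discharge after catheter removal requires that there be no subjective urinary complaint, and fistula testing before three months follows a complaint of incontinence (Secondary Outcomes).
   - Less exposed: ultrasound bladder volume, urine tests and the three-month cystography, which is done for all women.
7. **Work to be moved.** Inputs: 214 women and a 10% dropout allowance (Sample size), 21 months of recruitment (Recruitment procedure), and three scheduled entries per woman: day 3, discharge and three months (Secondary Outcomes).
   - All scheduled entries: 3 × 214 / 21 = 30.6 a month.
   - Three-month visit only: 214 / 21 = 10.2 a month. With dropout, 214 × 0.90 = 192.6, about 193, and 193 / 21 = 9.2 a month.
   - Unscheduled visits are not counted. A longer recruitment period would lower these rates.

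**The case against.** The strongest reply is that the Blinding section is itself the rule. It bars anyone who knows the group from doing follow-up, and the Project Management list, which mixes trial duties with manuscript roles, was simply not brought into line with it. Performing follow-up might also mean organising visits, with a different officer asking the questions. Part of this stands: a reader might infer that follow-up is planned to be unblinded, or that the theatre member interviews every woman, and the documents support neither. But the same entry also has this member conduct the survey after discharge, which is hard to read as mere organising, and nothing in the plan resolves the conflict.

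A second reply is that the effect is small. The women do not know their group and rate their own symptoms. Each problem is entered only once per woman, so one already recorded on the ward is not entered again later. The list linking numbers to groups is to be kept locked. All of this limits the exposure without removing it: a problem first reported after discharge still passes through whoever conducts that survey.

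Two other inferences should be resisted. One is that bladder injury, operative time or blood loss is biased by this conflict. They are recorded in theatre and not collected at follow-up, so their measurement is untouched. The other is that only dysuria and the Likert composite are exposed. Step 6 of the working shows that the reach is wider.

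**Conclusion.** The conflict is real. For the member who manages cystoinflation in theatre, the Blinding and Project Management sections cannot both be followed, and the ward surveyor's part in the random numbers file leaves ward blinding insecure as well. It is a failure to align the duty list with the blinding rule, and it should be corrected before the report claims blinded follow-up.

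The exposure covers interviewer-elicited follow-up data: mainly the secondary symptom outcomes, with adverse events, reported fever and complaint-driven steps alongside. Its size cannot be stated, because the plan does not say what share of women any one person interviews, and the bias cannot be computed from the documents. The conclusion assumes only that a person managing a visible procedure done in one arm learns who received it.

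**What to change.** Reconcile the two sections. Assign all symptom and adverse-event follow-up (day 3, discharge, unscheduled visits after discharge, and three months) to existing trained staff who have no theatre role for study cases and no part in preparing the random numbers file. Amend the entries of both the theatre member and the ward surveyor accordingly. Passing the theatre member's work to the ward surveyor would not be enough, because that person also helps prepare the file.

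The cost is redistributed work: about 31 scheduled entries a month, or about 9 to 10 if only the three-month visit moves. The smaller change would leave the ward interviews unsecured. Needing no extra staff is an assumption, since the documents do not confirm that trained officers without a theatre role exist.

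If duties cannot be changed, state in the Blinding section and in the report that follow-up assessment of symptoms and adverse events was not blinded. That costs one sentence in each place.
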